6.7 Outcome Research Assessment

Note: As of Protocol Version 7/ Amendment 6, quality of life assessments are no longer being performed.

Throughout the clinical trial period, patients will be asked about their quality of life via the Quality of Life questionnaires EQ-5D-5L.

The EQ-5D-5L is a standardized instrument developed by the EuroQol Group to describe and value health related quality of life. The instrument comprises the following five dimensions: mobility, self-care, usual activities, pain/discomfort and anxiety/depression. Each dimension is rated by the patients on a 5 point scale as having 'no problems' (a score of 1), 'slight problems (a score of 2), 'moderate problems', (a score of 3), 'severe problems', (a score of 4) and 'extreme problems', (a score of 5) based on descriptive examples: the scores are not intended to be summed. Present overall state of health is also to be rated on a vertical visual analogue scale (approximately 20cm in length) from 0 to 100 (the higher the number the better quality of life.

The EQ-5D-5L will be performed at screening (any time prior to first dose) and then monthly on Day 1 of Cycles 1 to 4 (completed prior to all other D1 procedures) for all Phase 2 patients.

Patients should self-complete the EQ-5D-5L and return to the site. Data will then be entered into the patient's eCRF.

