The imputation will be done according to methodology proposed by Diehr et al. (2007). Data will be imputed for missing assessments of Phase 2 patients and will be performed separately for each of five dimensions and VAS score of the EQ-5D-5L. VAS and each of the dimensions is represented by QOL in the imputation algorithm below. The five domains of EQ-5D-5L responses are ordered categories ranging from "no problems" to "extreme problems." Answers will be converted to a 5-point scale in which 1=no problems and 5= extreme problems. The VAS score of EQ-5D-5L ranges from 0 (worst health) to 100 (best health).

• Compute QOL-transformed (QOLt):

QOL score will be transformed to the probability that a person will have good QOL next cycle (have domain QOL \leq 3 next cycle; or have VAS QOL \geq 80), estimated from his QOL this cycle. All transition pairs (two values of QOL for the same person 1 cycle apart) will be used in the longitudinal data, and the transformation parameters will be estimated from a logistic regression of a binary variable "Good QOL 1 cycle later" on "QOL now." In the longitudinal data for each patient a column with one space for every cycle of that patient's potential follow-up will be created. The regression model will be as follows:

logit (Good QOL 1 cycle later) = a + b*QOL now.

The estimated probability of having good QOL 1 cycle later as a function of current QOL is then:

QOLt = Prob(Good QOL 1 cycle later | QOL) = exp(a+b*QOL)/(1+exp(a+b*QOL)).

• Compute QOL transformed with deaths added (QOLtd):

Set the values of QOLt for the cycles after a patient died to zero. For cycles after death, patients should receive a zero because they have no probability of having good QOL one cycle later.

• Compute QOLtd imputed (QOLtdi):

QOL for cycles when patients were alive but had no QOL data will be imputed from the regression of QOLtd on the logarithm of time from death (or time from the analysis date if still alive).

Calculation of time variable Cycle before death/end of follow-up (CBD):
 CBD = Cycle before death = cycle minus the integer part of (#days survived/28) + 1.

or

CBD = Cycle before end of follow-up = cycle minus the integer part of (#days on study/28) + 1

Unobserved cycles (e.g. due to missed visit, or time between last observed cycle and death when subject was alive but did not provide data) before deaths or end of followup will be imputed.

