2) Time variable CBD will be transformed to log form (LCBD) as below: LCBD=log(absolute value of CBD + 1)

- 3) A mixed model will be used to predict QOLtdi. The dependent variable is QOLtd; the mixed model will contain random intercept and slope subject effect, and fixed time effect (LCBD). QOLtdi will be predicted at imputed cycles.
- Compute QOLtdi re-transformed to the original scale (QOLback): This should be done by inverting the logistic regression equation.

QOLback = (logit(QOLt) - a)/b = [ln ((QOLt)/(1-QOLt)) - a]/b.

• Round imputed values up to the nearest whole number.

Note that no numerical values will be given after death, but "999" flags will be included to indicate cycles when patient was dead.

D. Multiple Study Centers

No stratification by the study centers will be utilized for analyses of efficacy or safety data.

E. Covariate Adjustment in Primary Analysis

Not planned for the primary analysis.

F. Sample Size Reassessment

No sample size reassessment is planned.

G. Interim Analyses

Interim analyses will be performed for the Phase 2 Cohort 1 and in other applicable Phase 2 cohorts that use two-stage designs, at defined timepoints, as outlined in section IV.C.

- Phase 2 Cohort 1: two interim analyses with 33% and 67% of patients' information respectively
- Phase 2 Cohort 2: with first 11 patients evaluable for response
- Phase 2 Cohort 6: with first 14 patients evaluable for response
- Phase 2 Cohort 7: with first 17 patients evaluable for response

• Phase 2 Cohort 8: with first 7 patients evaluable for response

As a result of these analyses, enrollment in a given cohort may be stopped early for futility, or in Cohort 1 for efficacy as well. Interim analyses that meet stopping criteria for futility are binding.

H. Multiple Comparisons

Alpha is controlled for the primary analysis within each Phase 2 cohorts. Corrections for multiple comparisons are not applied for the secondary or exploratory endpoints, as they are descriptive analyses.

I. Analysis Sets

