Line plots showing the mean (+/- SE) bone marrow blasts, ANC count, hematocrit, platelet count will be presented over time on Day 1 for cycles 1-15 for patients in the Phase 2 Cohort 1 FAS and EE analysis set by best response (CR/CRh, non-CR/CRh responders, and non-responders).

Efficacy Profiles

For IA2, For those patients who have a best overall response of PR or better, patient plots of ANC, platelet count, hemoglobin, and bone marrow blasts (analyzed as described above) will be produced for all patients in the Phase 2 Cohort 1 FAS and for patients in the Phase 1 FAS whose starting dose of FT-2102 was 150 mg BID.

C. Quality of Life Analysis

The EQ-5D-5L consists of five dimensions: mobility, self-care, usual activities, pain/ discomfort, and anxiety/depression. Each dimension has 5 levels of health state: no problems, slight problems, moderate problems, severe problems and extreme problems. The patient indicates his/her health state by selecting the most appropriate statement in each of the five dimensions. This decision results in a 1-digit number that expresses the level selected for that dimension. The digits for the five dimensions can be combined into a 5-digit number that describes the patient's health state. Present overall state of health is also to be rated on a vertical visual analogue scale (VAS) from 0 (worst health) to 100 (best health). This assessment was only performed on Phase 2 patients. EQ-5D-5L data will be summarized from the screening visit through cycle 8 for the FAS (Phase 2) and EE analysis sets (Phase 2).

Five domains of EQ-5D-5L

The number and percentage of patients reporting each score per dimension will be summarized, as well as the number reporting some problems on that dimension (score >1). Also, the change from baseline in the number reporting some problems in each dimension will be reported (raw and percent change). An additional summary table will be produced that summarizes the EQ-5D-5L data by best response (3 groups: CR/ CRh, Other Responders, Non-Responders). Missing data will be imputed as described in Section VI.C.

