A stacked bar chart will be produced to illustrate the domain values. In the chart, the x axis will represent nominal visit (screening, cycle 2, cycle 3, etc.) and the y axis will represent percentage. Each bar will add to 100% and be color coded to represent the percent of patients reporting each level (1-5) of problems within the dimension for that visit. A separate chart will be created for each of the dimensions. This figure will only be created for the

Phase 2, Cohort 1, EE analysis set. The figure will also be produced by best overall response, as described above for the summary table.

VAS score of EQ-5D-5L

The VAS score of overall state of health will be summarized by descriptive statistics (mean, standard deviation, median, Q1, Q3, minimum, maximum) by visit, as well as the number and percentage of patients reporting bad overall state of health (score < 80). An additional summary table will be produced to summarize change from baseline to first response for CR/CRh and Other Responders, or change from baseline to best score for non-responders, by descriptive statistics by best response (3 groups: CR/CRh, Other Responders, Non-Responders). Missing data will be imputed as described in Section VI.C.

All EQ-5D-5L data will be listed. In the listing, imputed data will be flagged.

XII. References

Atkinson EN and Brown BW. Confidence limits for probability of response in multistage phase II clinical trials. Biometrics 1985; 41 (3): 741-744.

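### VAS change is taken at first response for responders but at the best score for non-responders, which tilts the by-response table towards non-responders

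*SAP*

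**What the plan says.** SAP Section XI.C, under the VAS heading, plans VAS descriptive statistics by visit and then an additional table in three best-response groups: CR/CRh, Other Responders and Non-Responders. The time point depends on the group. For the first two the table gives "change from baseline to first response for CR/CRh and Other Responders". For the third it gives "change from baseline to best score for non-responders". The same section defines the scale as 0 for worst health and 100 for best, so the best score is the highest one.

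The documents differ on how many readings a patient can have. SAP Section XI.C states: "EQ-5D-5L data will be summarized from the screening visit through cycle 8". Protocol Section 6.7 states: "The EQ-5D-5L will be performed at screening (any time prior to first dose) and then monthly on Day 1 of Cycles 1 to 4". Missing VAS values are imputed under SAP Section VI.C.

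Quality of life is an exploratory objective. SAP Section VI.H says: "Corrections for multiple comparisons are not applied for the secondary or exploratory endpoints, as they are descriptive analyses". The SAP gives no reason for the two time-point rules and no alternative version of the table.

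**The concern.** Three groups stand side by side in one table, but their entries are different quantities. A responder contributes one reading, at a time set by the response. A non-responder contributes the highest of however many readings were taken. When the score varies from visit to visit, the highest of several readings sits above baseline on average even if nothing has changed. Part of any non-responder gain is then produced by the rule.

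Two readings of the table are affected. The contrast between responders and non-responders can look smaller than it is, or change sign. The non-responder entry, read alone in a study with no randomised control, can look like a quality-of-life benefit without a response.

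**Working it through.** The plan states no expected value for this table, so there is no figure of its own to reproduce.

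**Inputs from the documents**
- Responders: one reading, at first response (SAP XI.C).
- Non-responders: best reading, a maximum on a 0 to 100 scale (SAP XI.C). I take this to mean best post-baseline reading.
- Post-baseline readings, k: Cycles 2, 3 and 4 under Protocol 6.7, so k = 3 (Cycle 1 Day 1 is before dosing). Cycles 2 to 8 under SAP XI.C, so k = 7 if every cycle is assessed.

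**Inputs assumed, because the documents give neither**
- Total VAS SD, S: 15, 20 or 25 points.
- Correlation between visits, ρ: 0.3, 0.5 or 0.7.

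**Step 1: direction.** For any patient, max(Y1, …, Yk) ≥ Yj for every visit j. No distribution is needed. Only the non-responder rule uses the maximum.

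**Step 2: size in SD units.** Suppose no true change and exchangeable normal readings with within-patient SD w. The mean change to one visit is 0. The mean change to the best of k readings is w × m(k), where m(k) is the expected maximum of k standard normals:
- m(1) = 0
- m(3) = 3/(2√π) = 0.846
- m(4) = 1.03
- m(7) = 1.352

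**Step 3: illustration in points.** With w = S√(1 − ρ), the excess is S√(1 − ρ) × m(k).

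| Assumed S, ρ | w | k = 3 | k = 7 |
|---|---|---|---|
| 15, 0.7 | 8.2 | 7.0 | 11.1 |
| 20, 0.5 | 14.1 | 12.0 | 19.1 |
| 25, 0.3 | 20.9 | 17.7 | 28.3 |

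A simulation of 400,000 patients per scenario agrees to within 0.1 point. Holding scores within 0 to 100 (assumed mean 65, S = 20, ρ = 0.5) gives 11.4 and 17.9.

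**Step 4: non-responders who truly decline** (S = 20, ρ = 0.5, simulated).

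| Loss per cycle | k | Mean change over visits | Change to best score |
|---|---|---|---|
| 2 points | 3 | −3.9 | 8.1 |
| 2 points | 7 | −8.0 | 12.0 |
| 5 points | 3 | −10.0 | 2.7 |
| 5 points | 7 | −20.0 | 4.1 |

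The apparent gain shrinks as the decline steepens, but in these scenarios it still has the wrong sign.

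**Step 5: same rule in every group.** If all groups use a single matched visit, or the best score over the same visits, the artificial difference with no true effect is 0. Best score over unequal numbers of visits does not achieve this. Seven readings against three gives 1.35 − 0.85 = 0.50 w in favour of the group with more readings.

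**The case against.** **Non-responders have no first-response date, so some substitute was needed.** True, but the substitute need not be a maximum. A scheduled-cycle comparison needs no response date. The SAP's EQ-5D-5L domain bar charts already work this way, by visit and by best overall response.

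**The rule works against showing a responder benefit, so it is conservative.** For the contrast, that is a fair reading, although the SAP does not offer it. It is not conservative for the non-responder entry taken alone.

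**The table is exploratory, descriptive and untested.** This stands, and it sets the weight of the point. No decision or error rate in the documents depends on it.

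**Other quality-of-life outputs exist.** This stands in part. A reader might infer that the whole quality-of-life analysis is biased; the documents do not support that. VAS statistics by visit, an EQ-5D-5L table by best response under the five-domains heading, the bar charts (Cohort 1, EE set) and full listings are all planned, and none states a time-point rule that differs by group. But the VAS by-visit summary is not said to be split by response, and the by-response EQ-5D-5L table may not include VAS. No VAS summary by response on a common rule is clearly specified.

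**The SD figures assume too much.** This also stands. A reader might take 0.85 or 1.35 SD as the bias that will occur. Treatment failure is a listed reason for stopping treatment (Protocol Section 8.2.1), so many non-responders may have few readings, and with one reading the excess is zero. Missed cycles are filled with mixed-model predictions, and the described algorithm adds no residual noise, so imputed values would not act like independent draws. They can still be candidates for the maximum, and SAP Section VI.C rounds them up.

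**Conclusion.** The point holds. The two rules are not comparable, and the mismatch raises the non-responder change whatever the distribution of scores. The table can therefore understate or reverse the responder versus non-responder difference.

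The size is conditional. About 0.85 within-patient SD (k = 3) to 1.35 SD (k = 7) applies if there is no true change, readings are exchangeable and every non-responder has that many. The point values above rest wholly on assumed SDs and correlations.

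A reader might also infer that non-responders must come out ahead. That does not follow: a large responder benefit could still show, and short follow-up in non-responders reduces or removes the effect. Nor are responders measured at a fixed visit; first response falls at a different time for each patient, which is a further reason to compare by cycle.

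This is a minor point about one exploratory table. The primary CR/CRh analysis is unaffected.

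**What to change.** In SAP Section XI.C, replace the group-specific rule with VAS change from baseline at each scheduled cycle for all three best-response groups, with the number of patients at each cycle.

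If a single number is wanted, use the same summary in all three groups over the same cycle window, for example best score through a common cycle, and show the number of readings per group. Best score without a common window should not be used, because it would favour whichever group stays longer. State whether imputed values may count as the best score, and name the last cycle, since the protocol and SAP schedules differ.

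The cost is one table specification and no new data. SAP Section I allows changes until database lock; after that, the change can be documented as a deviation in the study report.

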Appendix 1 Schedule of Event

Study Procedures	Pre-	Screening					Cycl	e 1	-	-				Сус	cle 2	-		Cycle 3 and Beyond	End of Treatmentª	28-day Follow- up ^b	Survival Follow- up
Days	(Optional)	D1)	D1	D2	D5 ± 1D	D8 ± 1D	D12 ± 2D	D15 ± 2D	D19 ± 2D	D22 ± 2D	D26 ± 2D	D1 ± 2D	D2 ± 2D	D4 ± 2D	D8 ± 2D	D15 ± 2D	D22 ± 2D	D1 ± 3D	± 7D	+ 7D	q 3 mo
Signed Informed Consent ^e		X ^c																			
Complete Medical History ^{d}		Х																			
Concomitant Medications		X	Х	Xe		Х		Х		Х		Х				Х		Х	Х	Х	
Height and Weight ^f		Х	Х									Х						Х	Х		
Vital Signs ^g		Х	Х			Х		Х		Х		Х						Х	Х		
ECOG PS		Х	Х									Х						Х	Х		
Physical Examination		Х	Х			X ^{h}		X ^h		X ^h		$X^{\underline{h}}$				X ^h		$X^{\underline{h}}$	Х		
Serum or Urine Pregnancy Test ⁱ		Х	х									Х						Х	Х		
12-lead Electrocardiogram ⁱ		Х	Xi			Xi		Xi		Xi		Х				Xi		Х	Х		
Holter Monitoring (Phase 2 only) ^k			Х	Х								Х	Х								
Clinical Serum Chemistries ^{1, m}		Х	Х		X ⁿ	Х	X ⁿ	Х	X ⁿ	Х	X ⁿ	Х			X ⁿ	Х	X ⁿ	Х	Х		
CBC with Differential and Platelet Count ^{m.o}		Х	х		X n	Х	X ⁿ	Х	X ⁿ	Х	X ⁿ	Х			X n	Х	X ⁿ	Х	Х		
Coagulation Parameters ^p		Х										Х									
Bone Marrow Aspirate ^q		Х										Х						Х	Х		
Urinalysis ^{m, r}		Х	Х									Х						Х	Х		
Adverse Event Monitoring										C	ontinuo	us								X	
Pharmacokinetics (Peripheral Blood) ^s			Х	Х		Х		Х		Х		X ^t	Х	Х		Х		Х			

Study Procedures	Pre-	Screening					Cycl	e 1						Сус	cle 2			Cycle 3 and Beyond	End of Treatment ^a	28-day Follow- up ^b	Survival Follow- up
Days	(Optional)	(D -14 to D1)	D1	D2	D5 ± 1D	D8 ± 1D	D12 ± 2D	D15 ± 2D	D19 ± 2D	D22 ± 2D	D26 ± 2D	D1 ± 2D	D2 ± 2D	D4 ± 2D	D8 ± 2D	D15 ± 2D	D22 ± 2D	D1 ± 3D	± 7D	+ 7D	q 3 mo
Pharmacodynamics (Peripheral Blood) ^{u}	X⊻	Х	X	х		Х		Х		x		Х	X	X		Х		Х			
EQ-5D-5L (Phase 2 only)		X ^w										Х						Х	Х		
Study Drug Diary ^x			Х									Х						Х			
Study Drug Administration ^{y,z,aa}				D	rug wil	ll be gi	iven in a	accorda	nce wit	h the do	sing scl	hedules	for FT	-2102,	azacit	idine an	d LDA	С			
Survival ^{bb}																					Х

ALT = alanine aminotransferase; ALP = alkaline phosphatase; AST = aspartate aminotransferase; BUN = blood urea nitrogen; C1D1 = Cycle 1 Day 1; C2D1 = Cycle 2 Day 1; Ca = calcium; CBC = complete blood count; Cl = chloride; ECG = electrocardiogram; ECOG PS = Eastern Cooperative Oncology Group performance status; FSH = follicle-stimulating hormone; K = potassium; LDAC = low dose cytarabine; LDH = lactate dehydrogenase; LH = luteinizing hormone; MDS = myelodysplastic syndrome; Mg = magnesium; Na = sodium; PD = pharmacodynamic; PK = pharmacokinetic; PT = prothrombin time; PTT = partial thromboplastin time.

NOTE: All assessments will be conducted predose unless specified otherwise.

- ^a End of Treatment visit to be conducted within 7 days of the decision to discontinue treatment. End of Treatment assessments need not be repeated if they were completed within the previous 2 weeks (4 weeks for bone marrow assessments).
- ^b 28-day Follow-up visit to be conducted within 28 days (+ 7 days) of last dose for adverse event follow-up and to capture initiation of new therapies (conmedications).
- ^c Informed consent must be completed prior to the initiation of any study-specific procedures or assessments. The informed consent process may be completed prior to the Screening Period (i.e., before Day -14) (see Section 6.1.2 of protocol).
- ^d Includes complete surgical and cardiac history and complete leukemia or MDS medical history. Complete leukemia or MDS medical history will include applicable treatment history as well as cytogenetic risk categorization at diagnosis by NCCN or ELN guideline.
- ^e Only required in patients enrolled in Phase 1 and patients in Phase 2 participating in Holter monitoring.
- ^f Height at Screening only.
- ^g Includes temperature, blood pressure, pulse rate, and respiratory rate. Prior to dosing on Days 1, 8, 15, and 22 (Cycle 1); Cycle 2 predose on Days 1 and 15 and Cycle 3 and beyond predose on Day 1.
- ^h Symptom-directed physical examination due to specific findings or abnormalities.
- ⁱ To be performed on all female patients of childbearing potential and within 72 hr of dosing (Day 1 only of every cycle). At Screening, women aged 55 and under, are not surgically sterile, and who are amenorrheic must have LH, FSH, and estradiol measurements within the postmenopausal range for the

institution, to be considered of nonchildbearing potential. A serum pregnancy test is required at Screening; serum or urine pregnancy tests are allowed for post-Screening visits.

- ^j Phase 1: Electrocardiograms will be performed in a supine position in triplicate (within a 10-minute period) predose and at 2 (± 15 minutes), 4 (± 15 minutes), and 8 hr postdose (± 30 minutes) on Cycle 1 Day 1 and Cycle 2 Day 1, and predose at all study visits where indicated. Phase 2: Electrocardiograms will be performed in triplicate (within a 10-minute period) predose on Cycle 1 Day 1 and Cycle 2 Day 1, and at all study visits where indicated. All electrocardiograms will be performed in a supine position.
- ^k 24-hour 12-lead continuous Holters will be collected on C1D1 and C2D1 for patients at all centers in the US and select centers ex-US. The Holters should run from approximately 1 hour before dosing until 24 hours (the next day). Patients should remain supine for 10-15 minutes before and 5 minutes after ECG collection. See manual for further guidance on Holter monitoring.
- ¹ Clinical serum chemistries to include Na, K, Cl, bicarbonate, Mg, Ca, BUN, creatinine, AST, ALT, ALP, albumin, total bilirubin, direct bilirubin (collected only if total bilirubin is abnormal), LDH, glucose, amylase, lipase, uric acid, and thyroid function test (TFT) panel, which includes thyroid-stimulating hormone, free T3, and T4. In addition to the other chemistry panels, TFT panel is to be completed at Screening, C1D1, C2D1, and C3D1, then as clinically indicated.
- ^m May be performed from 48 hr (Cycle 2) or 72 hr (Cycle 3 and beyond) prior to Day 1 of a cycle (see Section 6.1 of protocol).
- ⁿ Clinical serum chemistries and CBC with differential and platelet count only at these study visits. May be performed through local laboratory testing.
- ^o Includes hemoglobin, hematocrit, platelets, and white blood cell count with differential.
- ^p Includes PT and PTT.
- ^q Bone marrow aspirate for clinical purposes and research to be done at screening, C2D1 (if no peripheral blasts), C3D1 (if not taken at C2D1), every one to two cycles until CR (not CRi or CRh) and then every two to three cycles until12 months after CR achievement, then at least every 6 cycles afterwards, End of Treatment, and at time of progression/relapse, per Response assessment guidelines (see Section 4.3 of protocol), For Phase 2 Cohort 2, bone marrow should be done at C2D1, C4D1, C6D1 and C12D1 then every 6 cycles thereafter. Refer to the laboratory manual for details of sample collection timing.
 - Local IDH confirmation may have occurred > 28 days prior.
 - C3D1 to be done on any patient who did not undergo a C2D1 bone marrow aspirate or biopsy.
 - Patients who discontinue study treatment for reasons other than treatment failure and have not withdrawn consent from overall study participation, should continue to be followed for disease response assessments until the time of disease progression/relapse or the initiation of a new treatment regimen. Patients who have stopped FT-2102 treatment for HSCT should continue to be followed until disease progression/ relapse. This information should be documented on the appropriate eCRF page
- ^r Urinalysis parameters include specific gravity, pH, total protein, protein, glucose, ketones, and blood. Microscopic examinations are to be performed as clinically indicated. For Cycle 3 & beyond and End of Study visit, urinalysis to be performed if clinically indicated.
- ^s Blood samples will be collected for measurement of plasma concentrations of FT-2102 (single agent) or FT-2102 + azacitidine (combination agent) Blood will be collected relative to FT-2102 administration as described in Section 6.4 and Table 4 of protocol
- ^t A 72-hour wash-out post C2D1 dosing will be requested from all patients participating in the dose-expansion stage. After the C2D1 FT-2102 AM dose, patients will be asked to refrain from taking FT-2102 until the AM of C2D4. PK samples will be collected on C2D2 and C2D4**.
- ^u Blood samples will be collected for PD biomarker analysis for single agent FT-2102 and FT-2102/azacitidine combination. Blood will be collected relative to FT-2102 administration as described in Section 6.5 and Table 5 of protocol.
- ^v Optional pre-screening blood sample for 2-HG level detection and IDH1 mutation testing (in 2-HG abnormal).
- ^w EQ-5D-5L survey can be completed anytime during screening prior to C1D1 dose.
- x Study drug diary should be distributed by the site to the patient on each cycle day 1, and collected at the next cycle day 1 visit

- ^y Single agent (FT-2102): FT-2102 will be given in accordance with dosing schedule × 28 days out of 28 days. On C1D1 only a single dose of FT-2102 is taken.
- ² Combination agent (FT-2102 + azacitidine): azacitidine will be administered via subcutaneous injection or intravenous infusion in combination with oral FT -2102 for 7 days, and then azacitidine will be stopped for 21 days; a 48-hr dose interruption of the azacitidine for weekends or holidays is allowed. On C1D1 and C2D1, azacitidine is to be administered immediately prior to FT-2102 (to enable consistent PK assessments). On all other days and cycles when FT-2102 and azacitidine are co-administered, it is recommended to dose FT-2102 prior to azacitidine.
- ^{aa} Combination FT2102 + cytarabine: cytarabine will be administered at a dose of 20 mg BID subcutaneously (SC) for 10 days every 28-day cycle
- ^{bb} After a patient discontinues study treatment and has completed their last study treatment visit, the study site will contact the patient approximately every 3 months to collect survival data and data pertaining to any other alternative anti-neoplastic therapy the patient begins for up to 12 months from the time of their 1st dose of study drug. Patients who discontinue for reasons other than disease progression or who withdraw consent will continue to be followed for response until progression occurs.
- * Not required in Phase 2 unless patient is participating in 24-hour Holter monitoring.
- ** Not required in Phase

